### **Endpoints**

The primary endpoint of the study is the occurrence of inhibitor development.

The secondary endpoints of the study are as follows:

- The annualized number of bleeding episodes per subject.
- The annualized number of spontaneous joint bleeding episodes per subject.
- The number of injections and dose per injection of rFVIII Fc required to resolve a bleeding episode.
- Assessments of response to treatment with rFVIII Fc for bleeding episodes, using the 4-point bleeding response scale.
- The total number of exposure days (EDs) per subject per year.

CONFIDENTIAL

The information contained herein may not be used, disclosed, or published without the written consent of Bioverativ Therapeutics Inc.

- Total annualized rFVIII Fc consumption per subject for the prevention and treatment of bleeding episodes.
- rFVIII Fc incremental recovery (IR)
- Response to ITI with rFVIII Fc (complete success, partial success, failure, early withdrawal)

Exploratory endpoints in the study include, but are not limited to

- Health Outcomes
- Investigator/Surgeon's Assessment of Response

Study Design:

An open-label, single-arm, multicenter study evaluating the safety and efficacy of rFVIII Fc in previously untreated pediatric subjects with severe hemophilia A when used according to local standard of care for implementation of a prophylaxis regimen, including an optional preceding episodic (on-demand) treatment regimen. The duration of episodic treatment is at the Investigator's discretion, in accordance with local standard of care. Surgery is allowed during the study. ITI is allowed during the study for subjects developing a positive inhibitor after exposure to rFVIII Fc. Separate consent is required before starting an ITI regimen. For subjects with inhibitors, the end of treatment will be defined based on the outcome of ITI therapy and the completion of any required tapering regimen and monitoring periods. The study will end after at least 90 subjects have reached at least 50 EDs with rFVIII Fc.

Subjects may be enrolled and receive study drug after samples for factor VIII activity and inhibitor testing at the central laboratory have been drawn, and diagnosis of severe hemophilia A with less than 1% factor VIII activity has been established based on local labs. However, any such subject must be withdrawn if the central laboratory screening results indicate factor VIII activity  $\geq 1\%$ , or a positive inhibitor.

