#### **6.2.2. Secondary Endpoints**

The secondary endpoints of the study are as follows:

- The annualized number of bleeding episodes per subject
- The annualized number of spontaneous joint bleeding episodes per subject

CONFIDENTIAL

The information contained herein may not be used, disclosed, or published without the written consent of Bioerativ Therapeutics Inc.

- Assessments of response to treatment with rFVIII Fc for bleeding episodes, using the 4-point bleeding response scale
- The total number of EDs per subject per year
- Total annualized rFVIII Fc consumption per subject for the prevention and treatment of bleeding episodes
- The number of injections and dose per injection of rFVIII Fc required to resolve a bleeding episode
- rFVIII Fc incremental recovery (IR)
- Response to ITI with rFVIII Fc (complete success, partial success, failure, early withdrawal)

For additional information about the correspondence between the objectives and their associated endpoints and assessments, see [Appendix E](#).

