### **16.2.3. Analysis of Efficacy Endpoints**

#### **Annualized Bleeding Episodes and Annualized rFVIII Fc Consumption**

Bleeding episodes during the efficacy period will be annualized on a per-subject basis and summarized by treatment regimen (episodic or prophylaxis regimen) and overall. This annualized bleeding rate (ABR) will be calculated as the total number of bleeding episodes experienced by a subject divided by the total number of days in their efficacy period for each treatment regimen or overall as appropriate, multiplied by 365.25. The per-subject ABR will also be summarized for type of bleed (spontaneous or traumatic), location of the bleed, and spontaneous joint bleeding episodes, and for other subgroups of interest. The consumption of rFVIII Fc will be annualized in a similar fashion and summarized overall as well as for subgroups of interest.

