### **16.5.2.3. Other Safety Parameters**

Clinical laboratory values will be summarized for change from baseline, shifts, and potentially clinically significant abnormalities. Threshold levels for potentially clinically significant laboratory abnormalities will be provided in the SAP. Listings of abnormal laboratory test results will be provided.

Vital signs will be summarized by the number and percentage of subjects with abnormalities. Abnormal values will be defined in the SAP. A listing of abnormal vital signs will be provided.

Duration of exposure and the total number of EDs to rFVIII Fc per subject will be summarized overall based on the Safety Analysis Set.

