2.2.2. Secondary Endpoints

The secondary endpoints of the study are as follows:

- The annualized number of bleeding episodes per patient (annualized bleeding rate [ABR])
- The annualized number of spontaneous joint bleeding episodes per patient.
- Assessments of response to treatment with rFVIII Fc for bleeding episodes, using the 4-point bleeding response scale.
- The total number of EDs per patient per year
- Total annualized rFVIII Fc consumption per patient for the prevention and treatment of bleeding episodes.
- The number of injections and dose per injection of rFVIII Fc required to resolve a bleeding episode.
- rFVIII Fc incremental recovery (IR).
- Response to ITI with rFVIII Fc (complete success, partial success, failure, early withdrawal).

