6.6.1. Exposure

6.6.1.1. Number of Injections and Exposure Days to rFVIII Fc

For any patient, the total number of days of exposure to rFVIII Fc will be accumulated from the time of their first on-study injection of rFVIII Fc. An ED is a 24-hour period in which one or more rFVIII Fc injections are given. The 24-hour window starts from the first injection on study and then for subsequent injections, it starts from an injection taken after/outside of a previously identified ED.

The total number of EDs on rFVIII Fc for each patient will be summarized categorically (<5, 5-<10, 10-<20, 20-<50, 50-<75, 75-<100 and >=100) and with descriptive statistics for the Safety Analysis Set.

The total number of injections per patient will be summarized overall and by reason for injection (prophylactic regimen, ITI regimen, spontaneous bleed, traumatic bleed, follow-up injection, surgical or other) using descriptive statistics for the Safety Analysis Set.

These tables will be presented by treatment regimen and for the inhibitor subgroups, as described in Sections 5.1.1.1 and 5.1.1.2 respectively.

The total number of injections and EDs will also be summarized by EPD entry compliance (see Section 6.6.2.3), <80% and >=80%, where >=80% is considered compliant.

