7.4.6. Total Number of EDs per Patient

The total number of EDs on rFVIII Fc for each patient will be summarized. This analysis is described in Section [6.6.1.1](#).

7.4.7. Total Annualized rFVIIIFc Consumption per Patient for the Prevention and Treatment of Bleeding Episodes

Total annualized rFVIIIFc consumption per patient for the prevention and treatment of bleeding episodes will be summarized for the FAS using descriptive statistics. See Section 6.6.1.4 for details on the annualized rFVIIIFc consumption derivation.

These tables will be presented by treatment regimen and for the inhibitor subgroups, as described in Sections 5.1.1.1 and 5.1.1.2 respectively.

7.4.8. Number of Injections and Dose per Injection of rFVIIIFc Required to Resolve a Bleeding Episode

The number of injections and average dose per injection (IU/kg) required to resolve a bleeding episode will be determined on both a per-bleeding episode and per-patient basis. For completeness, the total dose (IU/kg) administered to resolve a bleeding episode will also be determined on both a per-bleeding episode and per-patient basis. See Section 7.4.1 for details on the definition of a bleeding episode. A bleeding episode is considered resolved when treatment for the bleeding is no longer needed.

Per bleeding episode: The total number of injections will include the initial injection for a spontaneous bleed (SB), a traumatic bleed (TB), or a bleed of unknown type plus all injections identified as follow-up (FU) treatment for that bleed. For each bleed, the average dose per injection will be calculated as the average of all doses (IU/kg) administered among the SB/TB/Unknown and FU injections administered to treat that bleed; the total dose will be the sum of these doses. The number of injections required for the resolution of a bleeding episode will be summarized across all bleeding episodes both categorically (1, 2, 3, 4, >4; 1, >1; and ≤2, >2) and with descriptive statistics. The average dose per injection and total dose required for resolution of a bleeding episode will be summarized using descriptive statistics.

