12. LIST OF TABLES, LISTINGS, AND FIGURES

List of tables

Background/Demography
Summary of disposition by treatment regimen
Summary of disposition by inhibitor subgroup
Summary of disposition by inhibitor sub-classification I
Summary of enrollment by country and site by treatment regimen
Summary of patients attending key study visits
Summary of patients attending key ITI study visits
Summary of demographics and baseline characteristics by treatment regimen
Summary of demographics and baseline characteristics by inhibitor subgroup
Summary of demographics and baseline characteristics by inhibitor sub-classification
Summary of medical and surgical history by treatment regimen
Summary of hemophilia history by treatment regimen
Summary of bleeding history in the 3 months prior to study entry by treatment regimen
Summary of risk factors by inhibitor subgroup
Summary of physical examination at screening by treatment regimen
Summary of prior medications by treatment regimen
Summary of concomitant medications by treatment regimen
Summary of major protocol deviations by treatment regimen
Exposure/Dosing
Summary of injections and days of exposure to rFVIII Fc by treatment regimen
Summary of injections and days of exposure to rFVIII Fc by inhibitor subgroup
Summary of injections and days of exposure to rFVIII Fc by inhibitor sub-classification
Summary of injections and days of exposure to rFVIII Fc by EPD entry compliance by treatment regimen
Summary of duration of dosing with rFVIII Fc by treatment regimen
Summary of duration of dosing with rFVIII Fc by inhibitor subgroup
Summary of duration of dosing with rFVIII Fc by inhibitor sub-classification
Summary of duration of dosing with rFVIII Fc by EPD entry compliance by treatment regimen
Summary of prophylactic dose IU/kg
Summary of ITI dose IU/kg
Summary of prophylactic dosing interval
Summary of ITI dosing interval
Summary of annualized rFVIII Fc consumption (IU/kg) by treatment regimen
Summary of annualized rFVIII Fc consumption (IU/kg) by inhibitor subgroup
Summary of annualized rFVIII Fc consumption (IU/kg) by inhibitor sub-classification
Summary of last prescribed prophylactic dose and dosing frequency
Summary of compliance for the treatment of bleeding episodes by treatment regimen
Summary of prophylactic and ITI dose compliance

	Statistical Analysis Plan	Final v1.0
---	----------------------------------	-------------------

Summary of prophylactic and ITI dosing interval compliance

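### Exposure days per patient per year is a named secondary endpoint, but the SAP plans only total exposure days, with no time denominator

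*SAP*

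**What the plan says.** Three endpoint lists define a rate. The protocol synopsis has "The total number of exposure days (EDs) per subject per year", protocol Section 6.2.2 has "The total number of EDs per subject per year", and SAP Section 2.2.2 has "The total number of EDs per patient per year".

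The analysis sections plan a count. SAP Section 7.4.6, whose heading omits the per-year element, states "The total number of EDs on rFVIII Fc for each patient will be summarized" and points to Section 6.6.1.1. There, "The total number of EDs on rFVIII Fc for each patient will be summarized categorically", in bands from below 5 up to 100 or more, and with descriptive statistics, by regimen and inhibitor subgroup in the Safety Analysis Set. The matching output in SAP Section 12 is "Summary of injections and days of exposure to rFVIII Fc by treatment regimen", with counterparts by inhibitor subgroup, inhibitor sub-classification and diary-entry compliance. None is annualized.

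The gap starts in the protocol. Section 16.5.2.3 says that "the total number of EDs to rFVIII Fc per subject will be summarized overall based on the Safety Analysis Set". Section 16.2.3 annualizes bleeding episodes and adds "The consumption of rFVIII Fc will be annualized in a similar fashion", but does not mention EDs. SAP Section 10 lists three major differences from the protocol, and replacing the ED rate by a total is not among them.

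**The concern.** The planned analysis yields a different quantity from the named endpoint. The SAP's other per-year measures are worked out: the bleeding rate (7.4.3, carried through to bleed type and location in 7.4.4) and consumption (6.6.1.4) each have a formula ending in x 365.25. EDs per year has none.

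The total also carries limited information in this design. Under protocol Section 10.6, a patient not on ITI completes treatment after at least 50 EDs, so for completers the total is shaped by that rule. How often a child has to be infused is what a per-year figure would show, and it would go unreported.

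**Working it through.** The plan gives no figure for this endpoint, so there is none to reproduce. The check uses the SAP's own annualization form:

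EDs per year = EDs / days x 365.25

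**Inputs**
- 50 EDs: protocol Section 10.6
- Prophylaxis every 3 to 5 days: protocol Section 5.3
- Participation of about 6 months to 3 years: protocol Section 7.3; about 1 to 3 years: SAP Section 3.1
- Minimum evaluable efficacy period (1 day episodic, or 2 prophylactic injections): SAP Section 5.4.2
- Final prophylaxis period ends at the last dose: SAP Section 5.2.2

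**1. Same total, different rate, at the stated intervals**
- 3-day interval: 50 x 3 = 150 days; 365.25 / 3 = 121.75 per year
- 5-day interval: 50 x 5 = 250 days; 365.25 / 5 = 73.05 per year
- Ratio: 121.75 / 73.05 = 1.67

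Both patients have a total of 50 and fall in the 50-<75 band of Section 6.6.1.1.

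**2. Same total over the stated participation times** (illustrative: participation is taken as the denominator and each patient is assumed to have exactly 50 EDs)
- 6 months: 50 / 0.5 = 100 per year
- 1 year: 50 / 1 = 50 per year
- 3 years: 50 / 3 = 16.7 per year

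The spread is 6-fold on the protocol's range and 3-fold on the SAP's. Participation includes screening and follow-up, so these values somewhat understate on-treatment rates.

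**3. Does the by-regimen layout help?** It would split a switcher into, say, 10 episodic and 40 prophylactic EDs. Neither count is divided by time.

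**4. Behaviour of the rate if it is added over the efficacy period**
- Shortest periods: 1 / 1 x 365.25 = 365 per year; 2 injections 3 days apart give 2 / 3 x 365.25 = 244 per year.
- First-to-last-dose effect at a 3-day interval: 10 EDs span 9 x 3 = 27 days, so 10 / 27 x 365.25 = 135.3 against 121.75 (+11%). 50 EDs span 49 x 3 = 147 days, so 50 / 147 x 365.25 = 124.2 (+2%).
- If surgery or removed gaps break a 50-ED course twice, 47 intervals remain: 50 / (47 x 3) x 365.25 = 129.5 (+6.4%).
- PK-dose EDs should stay in the numerator. With an incremental-recovery dose every 4 weeks during ITI there are 365.25 / 28 = 13.0 a year. Dropping them from the numerator alone would turn daily dosing, 365 per year, into 352 (-3.6%).

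**The case against.** The strongest reply is that the mismatch is one of wording and the information is available anyway. Total EDs and dosing duration are both planned, by regimen and inhibitor subgroup, and Section 6.6.1.3 derives each patient's average prophylactic dosing interval, which would separate the 3-day patient from the 5-day one. Table shells and the exposure listing are not in the documents and might contain a rate. The endpoint wording does not mention the efficacy period, so EDs divided by dosing duration could also be called EDs per year. Nothing is tested, so the item could be closed by declaring the total-ED form in Section 10.

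Part of this stands. The 1.7-fold contrast is not hidden from every output, the participation ranges are illustrations, and not reported means not planned in the SAP text or output list. Totals above 50 are also expected, since Section 6.6.1.1 has bands for them.

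The rest does not remove the problem. Separate summaries of EDs and duration do not give the distribution of per-patient rates. The duration in Section 6.6.1.2 ignores interruptions. The average dosing interval uses only consecutive prophylactic doses not separated by a bleed or major surgery, so it omits EDs for treating bleeds and says nothing about episodic treatment. An unseen shell cannot be assumed to supply a rate the SAP never defines. The efficacy period is the SAP's own choice: Section 5.4.2 assigns it to efficacy endpoints, and Section 7.4.6 sits in the efficacy chapter.

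**Conclusion.** The concern holds. A secondary endpoint named in both documents has no planned analysis, and the section that should provide one summarises something else. One total of 50 EDs can stand for about 122 or 73 EDs per year at the protocol's prophylaxis intervals, and for 100 to 17 per year if 50 EDs are spread over 6 months to 3 years. The first range assumes regular dosing at the stated interval; the second assumes participation time as the denominator. The consequence is modest: the endpoint is descriptive, the ED and time data are already derived per patient, and no inhibitor, bleeding or consumption conclusion depends on it. It should be corrected before the analysis is run.

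**What to change.** In SAP Section 7.4.6 define, per patient:

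EDs per year = (EDs whose first injection falls within the efficacy period, end points included / days in that same period) x 365.25

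- Report it for the FAS by regimen and overall, and for the inhibitor subgroups used in Section 6.6.1.1. Label the overall figure as mixing daily ITI dosing with the other regimens.
- Count every ED as defined in Section 5.1.2.4, including PK-dose EDs inside the period. Surgical/rehabilitation periods, removed prophylaxis gaps over 28 days, and an episodic starter's time before 120 hours after the baseline PK dose then leave numerator and denominator together. State that the surgical exclusion follows Section 5.4.2.1 (major and minor), because Section 6.6.1.4 mentions major surgery only.
- Give the number of FAS patients without an evaluable efficacy period, and flag very short periods.
- Add the table to Section 12. Keep total EDs in the Safety Analysis Set as exposure data.

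The cost is one formula and one table from data already derived. The downsides are unstable values in very short periods and a small upward bias from periods that end at a dose: at a 3-day interval, about 2% for an unbroken 50-ED course, about 6% with two breaks, and about 11% for a period near 28 days. If the sponsor does not want the rate, the alternative is to rename the endpoint as total EDs and declare that in Section 10. That settles the inconsistency but gives up the per-year information.

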7.4.9. Response to Immune Tolerance Induction (ITI)

The ITI Analysis Set will be analyzed for response to the treatment regimen. Possible treatment responses are:

Complete Success

All of the following criteria are met:

1. Negative inhibitor titers in 2 consecutive determinations at least 28 days apart
2. IR $\geq 66\%$ of baseline in 2 consecutive determinations at least 28 days apart
3. $t_{1/2} \geq 6$ hours

Partial Success

The determination of partial success will be made only for patients who have completed 33 months of ITI but who do not fulfill the criteria for complete success. To achieve partial success, the following criteria must be met after patients have completed 33 months of ITI:

- Negative inhibitor titers on 2 consecutive determinations at least 28 days apart AND
- Either of the following (but not both):
 - IR $\geq 66\%$ of baseline in 2 consecutive determinations at least 28 days apart, or
 - $t_{1/2} \geq 6$ hours

Failure:

ITI failure is defined as the inability to meet criteria for Complete Success or Partial Success after 33 months on ITI.

Early Withdrawal/ITI Ongoing:

Patients may withdraw from the study during the ITI period before reaching 33 months or complete or partial success. In addition, any patients still in the ITI sub-study at the time of EoS or interim analysis will be included in this category.

Response categories of complete success, partial success, failure, and early withdrawal will be presented overall for the ITI Analysis Set, and separately for the inhibitor subgroups specified in Section 5.1.2.5, namely:

- Patients with high-titer inhibitors
- Patients with low-titer inhibitors that meet the clinically meaningful criteria
- Patients with high-titer inhibitors or low-titer inhibitors that meet the clinically meaningful criteria

Patients fulfilling the criteria for complete success will transition to a “tapering” regimen over a minimum period of 12 weeks with the aim of starting a prophylactic rFVIII Fc regimen, as described in [Section 10.2.7.5](#) of the protocol, and will be further monitored for relapse for up to 9 months as described in [Section 10.2.7.6](#) of the protocol.

During this period, the monitoring for relapse is via blood samples processed by the central laboratory using the Nijmegen-modified Bethesda assay for inhibitor detection, as well as IR assessments. The inhibitor titer and IR will be measured every 3 months during the follow up period. rFVIII Fc $t_{1/2}$ assessments will be performed 12 months after ITI success. If any of these tests reverse previously met criteria, at any time between the start of tapering through the beginning of prophylaxis, the tests must be repeated within 2 to 4 weeks to confirm relapse.

Relapse is defined as any of the following, occurring within 12 months following complete ITI success:

- A positive inhibitor (≥ 0.6 BU/mL using the Nijmegen assay) that is confirmed by a second test result of ≥ 0.60 BU/mL from a separate sample, drawn at least 2 weeks following the date that the original sample was drawn.
- 
- $t_{1/2} < 6$ hours.

The incidence of relapse during both the tapering and formal relapse monitoring period, in patients who are complete successes, will also be part of the summary.

A data listing will be generated for all patients in the ITI sub-study. This will include date of first inhibitor sample with a positive result, all inhibitor, IR, and $t_{1/2}$ measurements after commencement of ITI therapy, as well as dosing information. It will also include elapsed time to each assessment and a flag to indicate the patient’s ITI status.

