### 4.2.2.3. Schedule of Activities: Immune Tolerance Induction

The following schedule applies to subjects who are eligible for ITI, as described in Section 10.2.5.2. The specific follow up tests to be performed following ITI depend on the outcome of ongoing testing as described in Section 10.2.7.4 and Figure 2.

Activities	Pre-ITI Assessment (ITI Day 0)	Week 2 Visit (at 2 wks ±3 days)	ITI Visits		
			Every 4 Weeks (±2 Weeks)	Every 4 Weeks (±2 Weeks)	Every 4 Weeks (±2 Weeks)
			Starting at ITI Week 4, Until negative titer is confirmed	Starting at time of confirmed negative titer, Until IR ≥66% of expected is confirmed	Starting at time of IR confirmed ≥66 % Until ITI Complete Success a OR 33 Months of treatment
Informed Consent b	X				
Physical Examination	X	X	X	X	X
Weight (kg)	X	X	X	X	X
Vital Signs c	X	X	X	X	X
Hematology d,e	X		X	X	X
Blood Chemistry e,f	X		X	X	X
rFVIII Fc Dosing g	X	X	X	X	X
Nijmegen-Modified Bethesda Assay (Inhibitor Assay) h	X	X	X	X	X
Blood Sample for Exploratory Biomarker Characterization i	X		X	X	X
FVIII Activity for Incremental Recovery j			X	X	X
Half-life Evaluation (Factor VIII activity only to be done every 12 weeks once IR ≥66% confirmed) k					X l
Anti-rFVIII Fc Antibody	X	X	X	X	X
EPD Review, including rFVIII Fc Dosing Accountability m	X	X	X	X	X
Injection Site Inspection n	X	X	X	X	X
Adverse Events	<<<ONGOING; Monitor and record at all visits; telephone call every month>>>				

CONFIDENTIAL

The information contained herein may not be used, disclosed, or published without the written consent of Bioverativ Therapeutics Inc.

Serious Adverse Events	<<<ONGOING; Monitor and record at all visits; telephone call every month>>>
Concomitant Therapy/Procedures Recording o	<<<ONGOING; Monitor and record at all visits; telephone call every month>>>

AE = adverse event; DHA=Directions for Handling and Administration; EOT = end of treatment; ET = early termination; FVIII = coagulation factor VIII; ITI = immune tolerance induction; rFVIII Fc = recombinant coagulation factor VIII Fc fusion protein; SAE = serious adverse event.

- a See Section 10.2.7.4.2 for criteria for complete success.
- b Informed consent must be obtained prior to the ITI assessments beginning at Week 0.

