##### **10.2.7.4.2. Definitions of Complete Success, Partial Success, and Failure of Immune Tolerance Induction Therapy**

###### **Complete Success:**

CONFIDENTIAL

The information contained herein may not be used, disclosed, or published without the written consent of Bioerativ Therapeutics Inc.

Complete ITI success requires that all of the following criteria be met:

1. Negative inhibitor titers in 2 consecutive determinations at least 1 month apart
13. IR  $\geq$ 66% of expected in 2 consecutive determinations at least 1 month apart
14.  $t_{1/2} \geq$ 6 hours

Subjects may meet the criteria for complete success in less than 33 months.

Subjects fulfilling the criteria for complete success will transition to a “tapering” regimen over a minimum period of 12 weeks with the aim of starting a prophylactic rFVIII Fc regimen, as described in Section 10.2.7.5, and will be monitored for relapse for up to 9 months as described in Section 4.2.2.5.

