**Partial Success:**

The determination of partial success will be made only for subjects who have completed 33 months of ITI but who do not fulfill the criteria for complete success.

To achieve partial success, the following criteria must be met after subjects have completed 33 months of ITI:

1. Negative inhibitor titers on 2 consecutive tests within 2 months of each other

AND

15. Either of the following but not both:

- IR  $\geq$ 66% of expected

OR

- $t_{1/2} \geq$ 6 hours

If the subject has 2 negative inhibitor tests but recovery is  $<$ 66% of the subject’s baseline value (if known) [REDACTED], then the subject may remain on ITI at the discretion of the Investigator, up to a total duration of ITI of 33 months.

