**Failure:**

ITI failure is defined as the inability to meet criteria for Complete Success or Partial Success after 33 months on ITI.

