10. CHANGES TO PLANNED ANALYSIS

This SAP is based on Version 6 of the approved study protocol dated 12 February 2018. The major differences in the analysis described in this SAP compared to the protocol are:

- The Full Analysis Set consists of all patients who received at least 1 dose of rFVIIIIFc and were enrolled.
- An ITI Analysis Set and period was defined for the analysis of immune tolerance induction response data.
- The health outcomes questionnaire used in the study is not as specified in the protocol. The analysis described refers to that which was actually used and this can be found in [Appendix A](#)

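### SAP 7.4.9 defines ITI partial success by different titer and recovery rules from protocol 10.2.7.4.2 and does not declare the change, so the two documents can put the same subject in different response categories.

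*SAP*

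**What the plan says.** Response to ITI is a secondary endpoint in both documents (protocol 6.2.2, SAP 2.2.2). The SAP states that it is based on protocol Version 6, which is the version supplied, so neither text is superseded.

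Protocol 10.2.7.4.2 reserves partial success for subjects who have completed 33 months of ITI without complete success. Its titer rule is "Negative inhibitor titers on 2 consecutive tests within 2 months of each other". Its second condition is introduced by "Either of the following but not both" and offers IR at or above 66% of expected, or half-life of at least 6 hours. No second IR determination is mentioned. For complete success, the same section does ask for a repeat: IR at or above 66% "of expected in 2 consecutive determinations at least 1 month apart".

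SAP 7.4.9 gives the titer rule for partial success as "Negative inhibitor titers on 2 consecutive determinations at least 28 days apart AND" and the recovery limb as IR at or above 66% "of baseline in 2 consecutive determinations at least 28 days apart, or" half-life of at least 6 hours, again allowing only one of the two.

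The protocol makes failure the residual category: "ITI failure is defined as the inability to meet criteria for Complete Success or Partial Success after 33 months on ITI". The SAP defines it in the same way.

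SAP Section 10 opens with "The major differences in the analysis described in this SAP compared to the protocol are" and gives three items: the Full Analysis Set definition, the ITI Analysis Set and period, and the health outcomes questionnaire. The ITI item does not concern the response criteria.

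**The concern.** Two things change between the documents. A maximum gap between negative titers becomes a minimum gap, and a repeat IR determination is added. The added repeat resembles the complete-success rule carried over into partial success, although the protocol text asks for it only in the former.

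Since failure is residual, a subject who misses the partial-success rule after 33 months without complete success becomes a failure. The protocol has IR and half-life analysed in real time to support the ITI outcome (protocol 16.3), while the study report will follow SAP 7.4.9. A reader who takes the protocol's definition to interpret the reported categories could therefore misread them, and nothing in the SAP would give warning.

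**Working it through.** The plan states no figure to reproduce here. The check applies each rule literally to the same subject.

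**Inputs**
- Protocol titer rule: gap no longer than 2 months, taken as 2 × 30.4375 = 60.9 days; no minimum.
- SAP titer rule: gap of at least 28 days; no maximum.
- Protocol recovery limb: at least one IR at or above 66%. SAP recovery limb: two consecutive such values at least 28 days apart.
- Half-life limb: at least 6 hours in both. An unmeasured half-life is treated as not met.
- Both: exactly one of recovery and half-life; otherwise failure, unless complete success is met.
- ITI visits: "Every 4 Weeks (±2 Weeks" (protocol 4.2.2.3). Adjacent in-window visits can therefore be 28 − 28 = 0 to 28 + 28 = 56 days apart.

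**Titer rules alone.** They agree only for gaps of 28 to about 60 days. Below 28 days only the protocol rule is met; above about 60 days only the SAP rule is met.

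**Whole rule.** In each case the titer pair shown is assumed to be the only one available to satisfy the criterion.

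| Case | Titer gap | IR ≥66% | Half-life ≥6 h | Protocol text | SAP |
|---|---|---|---|---|---|
| a | 35 days | once | no | partial success | failure |
| b | 21 days | twice, 35 days apart | no | partial success | failure |
| c | 70 days | twice, 35 days apart | no | failure | partial success |
| d | 35 days | once | yes | failure | partial success |

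In case d the protocol's exclusive choice bars the subject, because both limbs are met, while complete success is also missed for want of a second IR. Under the SAP the single IR does not count, so only the half-life limb is met and the subject qualifies.

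**Can these cases arise?**
- Cases a and b can occur within the planned visits. In case a the half-life limb is seldom available: protocol 4.2.2.3 schedules the first half-life assessment 12 weeks after IR has been confirmed in 2 consecutive months, so a subject with a single qualifying IR would normally have no half-life value.
- Case c needs a missed or out-of-window visit, since 70 days exceeds 56.
- Case d is unlikely for the scheduling reason just given.

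**Size.** The documents do not give the number of ITI subjects. Assuming 10 to 20, one relabelled subject moves the partial-success and failure percentages by 100/20 = 5 to 100/10 = 10 points each.

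**The case against.** Several points on the other side carry weight.

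- **Figure 2.** The protocol says the outcome is assessed through the algorithm in Figure 2, which is not shown in the text available. Elsewhere (protocol 4.2.2.3 and 4.2.2.4) it treats IR at or above 66% as a confirmed state based on two determinations. The figure may require confirmation for partial success too. This stands as a limit: the IR conflict is with the protocol's written definition.
- **Reach.** The rule applies only after 33 months of ITI. Subjects still on ITI at study end go into the SAP's early-withdrawal/ongoing category, and the study closes once 90 subjects reach 50 exposure days. Few subjects may be affected. This stands.
- **Recoverability.** SAP 7.4.9 plans a listing of all inhibitor, IR and half-life results after the start of ITI, with elapsed times and a status flag, so the protocol rule could be re-applied by hand. This softens the consequence but does not declare the change.
- **Major differences only.** Section 10 claims to list only major differences. It does, however, record a small change to the Full Analysis Set definition, so a change to the categories of a secondary endpoint belongs there.

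Some stronger readings are tempting but unsupported. A reader might infer that the 28-day floor misclassifies about half of subjects. If visit dates were spread evenly over the ±14-day windows (an assumption), the gap would be 28 + U2 − U1 days, symmetric about 28, so about half of adjacent pairs would fall short. That is a per-pair figure. A subject on ITI for 33 months has many pairs, and neither document says that only the last counts. Under the same assumption the chance that k successive gaps all fall short is 1/(k+1)!, which is 1/6 = 17% for two and 1/24 = 4% for three. The protocol's own complete-success rule also sets a floor of 1 month on the same visits. A reader might also infer that the SAP moves subjects only towards failure; cases c and d go the other way. Nor do the documents plan a second, site-assigned response table that would compete with the SAP's.

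The contrast between recovery relative to expected and relative to baseline is not a conflict: protocol 10.2.7.4.1 takes the subject's own baseline as the reference where it exists, its alternative is redacted, and SAP 5.1.4 uses an absolute value when baseline is missing.

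**Conclusion.** The point holds: SAP 7.4.9 is wrong as written. Its partial-success criteria differ from the protocol text in both the titer and the recovery limb, the difference can change a subject's category in either direction, and Section 10 does not record it.

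The consequence is modest. It touches a descriptive secondary endpoint, only in subjects who complete 33 months of ITI without complete success, and leaves the primary endpoint alone. The 5 to 10 points per relabelled subject rest on an assumed ITI set of 10 to 20; the documents support no estimate of how many subjects would be relabelled. Confidence is high on the titer limb and somewhat lower on the IR limb, because Figure 2 could not be checked.

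**What to change.** Reconcile the two passages in one of two ways:

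1. Use the protocol's partial-success wording, as it stands, in SAP 7.4.9, without adding conditions that appear in neither document.
2. If the SAP's rule is intended, list and justify it in SAP Section 10, and tabulate ITI response under both definitions.

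In either case, confirm that Figure 2 agrees with the wording retained.

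The cost is a wording edit and, under the second option, one extra column in the summary of ITI response and relapse. The results needed are already in the planned ITI listing, so no new data are collected.
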